## **Statement of the risks/benefits for the study subjects.**

**How privacy, confidentiality** and the rights of human subjects will be protected. In order to safeguard the privacy of study participants, protected identifiers (e.g., a person's name) normally should not be recorded on the same instrument where you record data obtained from study subjects. A justification must be made in the protocol as to why the research cannot be conducted in any other way if you believe you need both protected identifiers and information obtained from subjects on the same data collection form.

For Aim 1, study participants will be interacting with a research team member to test a prototype of the I-HoME intervention. Feedback about the prototype intervention (I-HoME) along with private identifiable information will be collected via questionnaires and audiotaped interviews from home hospice patients, CGs, and providers. Data will be collected individually, in-person or via video conference. Patients who opt for participation via videoconference (e.g., Zoom) will be able to sign an electronic consent through Weill Cornell's REDCap database (see example of a consent form using this link

[https://redcap.ctsc.weill.cornell.edu/redcap\\_protocols/surveys/?s=RD7NHHK3P9](https://redcap.ctsc.weill.cornell.edu/redcap_protocols/surveys/?s=RD7NHHK3P9)). While there is a small risk of breach of confidentiality, we will take steps to minimize the risk. Data obtained from participants' feedback of the I-HoME intervention will be stored on the REDCap database, a secure web-based application hosted by the Weill Cornell Clinical and Translational Science Center. Demographic and survey data collected at the subject's home will be entered into REDCap while on-site in order to eliminate the risk of stolen or lost data during transportation. Data from interviews that cannot be stored on REDCap will be tape recorded and transferred to the PI's password protected computer which is protected on Weill Cornell Medicine's secure server. For interviews being conducted at the subject's home, an encrypted audio recorder will be used to reduce risk of data being accessed if stolen.

For Aims 2 and 3, all study participants will be interacting with a research assistant while those in the intervention group will also be interacting with a nurse interventionist delivering the I-HoME intervention. Human subject involvement will include data collected from home hospice patients, CGs, and providers by a research assistant. Data will be gathered via: (1) initial baseline assessment done in-person, (2) questionnaires administered by telephone or online via a REDCap weblink during the course of 6 weeks, (3) post-intervention questionnaires administered by telephone or online via a REDCap weblink 4 weeks post-intervention and (4) the patient's medical record. The patient's medical records will be reviewed by the RA at the beginning of the study to collect demographic data and at the conclusion of the study to collect post-intervention data. Private identifiable information will be collected and data will be linked to living individuals. Only members of the research team will have access to the materials.

While there is a small risk of breach of confidentiality, we will take steps to minimize the risk for participants in Aims 2 and 3. The I-HoME software will be provided by Doxy.me, which provides a secure HIPAA compliant platform to conduct synchronous video visits. Data collected for Aim 2 and 3 will be stored on the REDCap database. Precautions will be taken to protect the security of the data collected and the privacy of the individuals from whom we collected the data. All protected identifiers will not be recorded on the same instrument where record data will be obtained from study subjects. Demographic and survey data collected at the subject's home will be entered into REDCap while on-site in order to eliminate the risk of stolen or lost data during transportation. For interviews being conducted at the subject's home, an encrypted audio recorder will be used to reduce risk of data being accessed if stolen.

There is a minimal risk of subject distress during the administration of surveys (see Appendix B) to patients and CGs during the pilot phase in Aims 2 and 3. As a result, I will have safeguards in place to address subject's distress. All study subjects will be free to refuse to answer any questions or to discontinue study participation at any time. In all cases where there might be concerns for suicidality, referrals to a hotline and mental health services will be provided. In addition, the PHQ-9 will be administered to the subject. If subjects do not answer "not at all" to question 9 in the PHQ-9 survey, the research team member will remain with the participant and call to a trained professional to speak with the participant to create a safety plan which may include a call to 911 if warranted.

For studies that require a DSMB, a **DSMB plan** should be provided in the protocol which should include: number of members, meetings (how often), data that will be reviewed during the meetings and plan regarding dissemination of summary reports (i.e. meeting minutes) to the IRB.

## DATA AND SAFETY MONITORING PLAN

### PI of Grant: [name], MS

Grant Number: 1K76AG059997-01A1

**Title:** Developing and piloting a multi-component technology-based care intervention to address patient symptoms and caregiver (CG) burden in home hospice.

**Brief Description of Intervention:** This proposal aims to develop and evaluate a multi-component technology-based care intervention, i.e., Improving Home hospice Management of End of life issues through technology (I-HoME), that focuses on assessing and addressing patient symptoms and CG burden in the home hospice setting through synchronous live video visits and educational videos.

**NIH Phase III Clinical Trial?** No

**Multiple Site Trial?** No

#### Specific Aims:

**Aim 1:** Employ an iterative user-centered design process to develop I-HoME, a multi-component technology-based care intervention, for home hospice patients and their CGs. Development of I-HoME will incorporate best care practices and evidence-based management along with feedback from key stakeholders, i.e., patients (N=10), CGs (N=10), and hospice providers (N=10), to inform and refine the intervention.

**Aim 2:** Conduct a single armed (N=10 dyads) pilot study with a focus on optimizing data collection protocols and the intervention.

**Aim 3:** Conduct a randomized pilot study to evaluate the feasibility and potential efficacy of I-HoME (N=50) compared to usual care (N=50). Feasibility will be assessed by examining overall accrual, attrition, adherence to the study protocol, and use of the intervention; efficacy will be assessed using patient (symptoms), CG (burden, depression, anxiety, satisfaction with care), and systems (hospice live discharges, hospitalizations) outcomes.

#### Brief Description of Project Design

For Aim 1, ten home hospice providers (e.g., nurses, nurse practitioners, physicians) along with ten home hospice patients and their ten family CGs will be interviewed individually and recruited from the Visiting Nurse Service of New York (VNSNY) to provide feedback on the I-HoME intervention.

For Aim 2, ten patient/caregiver dyads will be recruited for the i-HoME intervention which will be delivered for up to a 6-week period. Based on the data gathered from the single armed pilot study, modifications will be made to the data collection protocols and intervention prior to moving on and conducting the pilot RCT.

For Aim 3, 100 patient and CG dyads will be recruited from VNSNY and randomly assigned, by hospice team, to either I-HoME (n=50) or to standard home hospice care (n=50) for twelve weeks. Feasibility and potential efficacy measures will be administered at baseline and in weeks 1, 2, 3, 4, 5 and 6. Post-intervention measures will be collected at the end of the intervention 4 weeks after a patient's death.

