### **Aim 3: I-HoME pilot RCT**

For Aim 3, 100 CGs will be recruited from VNS Health hospice teams. The intervention will be randomized by nurse. Therefore, CGs of certain nurses will receive the I-HoME intervention (n=50) for up to six weeks while others will be recruited to receive standard home hospice care (n=50). Feasibility and potential efficacy measures will be administered at baseline and after each visit/weekly (timeline may change based on results obtained from Aim 2). Baseline measures will be collected during the in-home visit or via phone call by the research team and subsequent measures will be collected via phone call or electronic survey.

**Intervention.** CGs randomized to the intervention group will have access to live synchronous video visits with a research nurse interventionist on a scheduled (weekly) and as-needed basis (hours will be dependent on funding). The study team will either make an in-home visit or conduct a phone call with the CG (based on CG preference) at the start of the study to obtain consent and train the CG on the I-HoME intervention. This group will be educated about I-HoME and learn how to use the tablet to access videos and communicate with the interventionist. Participants will also be given a laminated user guide/help card and have access to technical assistance if hardware or software concerns arise or if an adverse event occurs. Software by Doxy.me will be used to conduct HIPAA compliant synchronous video visits. Participants in this study will continue to receive standard home hospice care in addition to the I-HoME intervention. Phone visits will be conducted if video visits are unable to be done due to hardware or software issues.

**Standard Care Control.** Participants in the standard care control group will receive home hospice services as usual. They will also receive a tablet with hospice resources. These participants will complete the same measures as participants in the intervention condition on the same timeline using identical assessment procedures.

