**Aim 3:** For the pilot RCT, I will be collaborating with VNS Health home hospice teams (each team consists of 5-7 nurses). These two teams will be randomized to receive the intervention (I-HoME) or standard care at the nursing level. Since this is a pilot study and the primary aim is to assess for intervention feasibility, we acknowledge that we will not be able to control for certain differences. We will work with VNS Health hospice leadership to select hospice teams that serve similar patient populations. In both hospice teams, family CGs will be screened for study eligibility within 7 days of their home hospice admission through chart review. Screening will be conducted regularly by the research team. Prior to reaching out to potential participants, the

research team will contact the nurse caring for the patient and CG to confirm that it would be appropriate to contact the CG for the study. Weill Cornell and VNS Health are co-engaging one or more research staff through a subaward – they will be hired by VNS Health and performing the initial screening/recruitment. VNS Health staff will contact subjects by phone to inquire about their interest in participating (see telephone script C and D). If there is interest expressed by the CG over the phone, a research team member will reach out to conduct an in-home visit to describe the study and obtain written informed consent.

No external investigators (unless they are a VNSNY employee or VNSNY volunteer/intern) will be given names or contact information until subject approval is obtained through a VNSNY provider.

Hospice patients (n=20) will be referred by caregivers that are enrolled in the study. The study team will ask the caregiver (after they have been consented) if the patient would be open to participating in the study to provide ratings on their symptoms. Patients with a hospice diagnosis of dementia not be considered for the study. Eligible patients will be contacted by phone by a research team member.

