## Brief overview of analytic methods.

Feasibility will be assessed by examining accrual rates, attrition rates, adherence to the study protocol, hardware/software issues, and use of the intervention (e.g., frequency and duration of visits, number of educational video views). A feasibility questionnaire will be administered at the end of the intervention to CGs and to patients (if alive).

To measure potential efficacy, we will use mixed models (MMs) to analyze specific outcomes (i.e., symptoms, CG burden, hospitalization, etc.). MMs do not assume that each subject will contribute data at all-time points and so they can be used for data with complex attrition patterns. In these models, the subject's initial status (intercept) and the change in their status (slope) will be treated as random effects. The variables of group, time, the interaction of group and time, and any variable that differs between the two conditions at baseline or other variables of theoretical interest, expectation for inclusion in models from the literature, or near significance of difference by conditions will be modeled as fixed effects. Nurses will be examined in models as levels of a random classification factor. For all variables, four models will be tested: a linear effect of time, a log-linear effect of time allowing for more rapid change at the beginning of the study, a quadratic effect of time with no random slope for the quadratic term, and a quadratic effect of time with the slope of the quadratic term also being allowed to be random. Model selection will be done using the Bayesian Information Criterion, a measure of model misfit with a penalty added for extra parameters, with inferences only being made from the best fitting model. We will also test for a random intercept and random effect of time by hospice nurse to control potentially for nesting by nurse. Given the small number of hospice nurses we anticipate to be involved in the study, we do not expect either random effect to be statistically significant and plan to drop it from the model if it is not. We will also test for effects in CGs who are bereaved very early in the study.

Mixed model analysis will be conducted on seven outcomes.

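### Aim 3 states its unit of randomisation inconsistently (hospice team in the monitoring plan, nurse elsewhere) and does not say how team enters allocation or analysis

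*Combined protocol and SAP*

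**What the plan says.** Three current sections describe the Aim 3 allocation, and a fourth describes the analysis.

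- **Data and Safety Monitoring Plan, Brief Description of Project Design:** dyads are "randomly assigned, by hospice team", 50 to each arm, with a stated duration of twelve weeks.
- **Aim 3: I-HoME pilot RCT:** "The intervention will be randomized by nurse".
- **Procedures for recruiting study subjects, Aim 3 paragraph:** "These two teams will be randomized to receive the intervention (I-HoME) or standard care at the nursing level". The same paragraph gives the team size ("each team consists of 5-7 nurses") and confirms the number of teams ("In both hospice teams, family CGs will be screened for study eligibility"). It adds that some differences cannot be controlled, and that hospice leadership will help choose teams with similar patients.
- **Brief overview of analytic methods:** "Nurses will be examined in models as levels of a random classification factor". The nurse random intercept and nurse random time effect are then tested: "we do not expect either random effect to be statistically significant and plan to drop it from the model if it is not". Team is not named as a model term.

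None of these sections gives the number of nurses to be randomised, the method of randomisation, or whether allocation is balanced within team.

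**The concern.** Allocation by team and allocation by nurse are different trials. With two teams, allocating whole teams puts one in each arm. Any difference between the teams in patients, staffing or practice then cannot be told apart from the effect of I-HoME. Allocating nurses gives 10 to 14 clusters, and a between-arm comparison is possible.

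A second question remains under nurse allocation. Team is known before randomisation and may be related to outcome. If nurses are not allocated within team, the arms can differ in their mix of teams by chance, and no named model term would adjust for it.

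At stake is the potential-efficacy half of Aim 3, which the plan intends to analyse with mixed models on seven outcomes. The feasibility measures (accrual, attrition, adherence, use of the intervention) mostly do not rest on a comparison between arms.

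**Working it through.** **Inputs from the documents.** Two teams; 5 to 7 nurses per team; 50 caregivers per arm. The plan states no figure that depends on the unit of randomisation, so there is none to reproduce. It gives no intracluster correlation (ICC) and no alpha. Below, two-sided alpha 0.05 and ICCs from 0 to 0.10 are assumptions.

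**1. Allocation by team.** Clusters per arm: 2 / 2 = 1. Degrees of freedom for between-team variation: 2 clusters − 2 arms = 0. The between-team variance cannot be estimated, and no sample size changes that. The nurse random effect does not help, because every nurse in a team would be in the same arm.

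Suppose an individual-level test ignored team, with n = 50 per arm. Its type I error would be 2 × (1 − Φ(1.96 / √(1 + n × ICC / (1 − ICC)))):

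| Assumed ICC | n × ICC / (1 − ICC) | Type I error |
|---|---|---|
| 0 | 0 | 0.05 |
| 0.01 | 0.505 | 0.11 |
| 0.02 | 1.020 | 0.17 |
| 0.05 | 2.632 | 0.30 |
| 0.10 | 5.556 | 0.44 |

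**2. Allocation by nurse.** Clusters: 2 × 5 = 10 to 2 × 7 = 14. Degrees of freedom: 10 − 2 = 8 to 14 − 2 = 12. With a team fixed effect, these become 7 to 11.

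**3. Chance imbalance of team under unrestricted nurse allocation.** Assume 12 nurses (6 + 6), with 6 allocated to each arm. The number of possible allocations is C(12,6) = 924.

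| Split of each team between arms | Count | Probability |
|---|---|---|
| 3:3 | C(6,3)² = 400 | 43.3% |
| 4:2 either way | 2 × 15 × 15 = 450 | 48.7% |
| 5:1 either way | 2 × 6 × 6 = 72 | 7.8% |
| 6:0 either way | 2 | 0.2% |

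Any unequal split: (450 + 72 + 2) / 924 = 524/924 = 57%. A split of 5:1 or worse: (72 + 2) / 924 = 74/924 = 8%.

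**4. Allocation within team.** With 6 nurses per team, every team splits 3:3 and both probabilities become 0. With 5 or 7 nurses, a team splits 3:2 or 4:3, so a one-nurse difference remains. Balancing nurses does not guarantee balanced caregiver numbers, because enrolment per nurse may vary.

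**The case against.** The strongest reply is that the plan is really a nurse-randomised trial with one summary sentence left unrevised. The design, recruitment and analysis sections all point to the nurse. The monitoring plan's sentence also gives a different duration from the Aim 3 design section (twelve weeks against up to six), and its list of aims stops before Aim 4. This stands: nurse allocation is the more likely intention. The inconsistency still needs removing. The monitoring plan is current text that the safety monitor is asked to review, and the recruitment sentence itself makes the teams the thing randomised before qualifying it.

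A reader might infer that the trial has one cluster per arm and therefore no valid comparison. The documents do not support that as a description of the trial. It follows only if the monitoring plan's sentence is what was carried out, and even then it concerns efficacy only. The plan calls itself a feasibility trial.

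A reader might also infer that nurses are randomised without regard to team. The documents are silent on this, and the recruitment wording is compatible with allocation within team. The 57% and 8% describe unrestricted allocation of an assumed 6 + 6 nurses, and most of the 57% is the mild 4:2 split.

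Two further points stand in part. Choosing teams with similar patients reduces the likely team effect, though it does not remove it. The analysis section also admits covariates that differ at baseline or are of theoretical interest, so team could enter by that route. That leaves its inclusion to a later decision. Finally, the Aim 2 recruitment paragraph ties teams to regions of the city, but the Aim 3 paragraph does not repeat this, so confounding with region is not established.

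**Conclusion.** The concern holds as an inconsistency that should be fixed; it does not show a failed design. One current section allocates by team, while the others allocate and model by nurse.

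- **If teams were allocated whole:** one cluster per arm and 0 degrees of freedom, so the between-arm efficacy comparison is fully confounded with team. An individual-level test that ignored team would have a type I error of 0.11 to 0.44 for assumed ICCs of 0.01 to 0.10.
- **If nurses were allocated, as is probable:** 10 to 14 clusters, and a comparison is possible. What remains is that allocation within team is unstated and no team term is named. Under the 6 + 6 assumption with unrestricted allocation, the chance of an unequal team split is 57%, and of 5:1 or worse 8%.

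The direction and size of any resulting bias cannot be given, because the documents contain no estimate of how far the teams differ.

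**What to change.** 1. Reconcile the monitoring plan's design description with the Aim 3 design, recruitment and analysis sections, naming the unit actually used. The two durations in those passages should be reconciled in the same edit. Cost: wording.
2. If the unit is the nurse, state the number of nurses and the randomisation method, and allocate nurses within each team as evenly as possible. This costs nothing for a list of 10 to 14 nurses. It applies only where allocation is still to be done: the Aim 4 section already refers to attrition in collected data, so Aim 3 may be past this point.
3. In either case under nurse allocation, report nurses and caregivers by team and arm, and prespecify team as a fixed effect in the outcome models. Cost: one degree of freedom.
4. If teams were in fact allocated whole, label the between-arm efficacy results descriptive only. The feasibility reporting can stay as planned.

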## A. PARTICIPANTS SAFETY

### A.1 Adverse Event and Serious Adverse Event Collection and Reporting

I have identified two categories of adverse events: serious adverse events and safety alerts. Members of the research team will be trained to track these events through participant self-report and/or interactions with participants. Pre-intervention adverse events are issues that are identified and recorded by study personnel during interview discussions and are unrelated to the intervention. Adverse events are situations that occurred during the intervention period and are identified by members of the research team during any follow-up assessment or any off-protocol interaction with a participant. Adverse events occur anytime following randomization until study completion. Safety alerts will be identified during any interview or anytime following randomization until study completion.

Below are the specific events that trigger a formal response:

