**Measurements.** All participants will be assessed on the measures listed in Table 2 (see **Appendix B** for more details). Measures will be administered at baseline and in weeks 1, 2, 3, 4, 5 and 6. Validated surveys will be administered via phone by a research assistant. Post-visit measures for caregivers will be collected during each interview, and additional measures will be collected during the final interview. Participants will be compensated \$50 for an initial baseline survey followed by \$25 (by ClinCard) each time they complete a within study phone call/electronic survey. Post-intervention measures for patients will be collected from their medical chart in both groups. For the intervention group, the collection will start from study enrollment to 4 weeks after the final I-HoME intervention visit or the date of program end (which ever one is earlier). For the control group, the collection will start from study enrollment to 11 weeks after enrollment.

Table 2.

Baseline measures		Post-intervention measures	
Patient (from medical chart)	Caregiver	Caregiver	Patient
Age	Age	Burden	Hospice discharge reason
Gender	Gender	Depression	Use of non-home hospice services (inpatient care, respite care)
Race/ethnicity	Race/ethnicity	Anxiety	Number of nursing visits
DNI/DNR status	Religion	Software issues	Number of social work visits
Medications	Education	Hardware issues	Number of chaplain visits
Comorbidities	Relationship to patient	Patient symptoms	
Hospice diagnosis	Hours providing care to patient	CaSES	
	Number of CGs caring for the patient	Caregiver (Final Interview)	
	Occupation	CG Satisfaction	
	Income	Feasibility questionnaire	

### Addition of patient participants for Aim 3

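### Adverse events are found through contact with no scripted query described, and contact is heavier in the I-HoME arm, so recorded counts may differ by arm and control events may be missed.

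*Combined protocol and SAP*

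**What the plan says.** Section A.1 of the Data and Safety Monitoring Plan sets out how events are found: "Members of the research team will be trained to track these events through participant self-report and/or interactions with participants". Adverse events are those "identified by members of the research team during any follow-up assessment or any off-protocol interaction with a participant". The listed serious events all concern the caregiver: hospitalization, institutionalization, emergency room visit and death. A severe medical problem of the caregiver is listed as a safety alert.

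The Aim 3 section gives both arms one survey schedule: "Measures will be administered at baseline and in weeks 1, 2, 3, 4, 5 and 6". Of controls it says: "These participants will complete the same measures as participants in the intervention condition on the same timeline using identical assessment procedures". Table 2 lists the measures. For caregivers it includes software and hardware issues, burden, depression and anxiety, but none of the listed medical events. The chart review after baseline covers patients only. The Aim 3 measurements text has a research assistant give the surveys by phone, but the same section also allows electronic surveys. The risk/benefit section likewise describes "questionnaires administered by telephone or online via a REDCap weblink during the course of 6 weeks".

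Contact beyond the surveys differs by arm. I-HoME caregivers have "live synchronous video visits with a research nurse interventionist on a scheduled (weekly) and as-needed basis". They also "have access to technical assistance if hardware or software concerns arise or if an adverse event occurs". Apart from usual care and the shared measures, the control paragraph says only: "They will also receive a tablet with hospice resources".

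**The concern.** If no fixed question asks about an event, whether it is recorded depends on how often someone on the team talks with the caregiver and whether the subject comes up. The I-HoME arm has more such occasions by design. For the same true risk, it may then show more events, while events in controls go unrecorded.

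Two things are at stake. First, a missed control event is a safety gap in itself. Second, section C.1 puts adverse-event summaries in the monitoring report. Section C.7 lets the closed session see data by study group, unblinded if necessary, and requires a recommendation to continue or terminate at every meeting. With 50 caregivers per arm, counts will probably be small, and one or two events can change the picture. An excess in I-HoME could be a detection artefact, and a true excess could be explained away as better detection. Without the source of each event, the monitor cannot tell which.

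**Working it through.** The plan gives no event rate or detection rate, so there is no stated figure to reproduce. The check counts contacts and then runs an illustrative detection model.

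**Contacts for a caregiver with a full course (Aim 3 section)**
- Shared assessments: 1 baseline + 6 weekly = 7 in each arm.
- Nurse visits: about 6 scheduled in I-HoME, 0 in control.
- After baseline: 6 in control and 6 + 6 = 12 in I-HoME, before as-needed visits and assistance contacts.

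**Model (all rates below are assumptions)**
- The true risk is the same in both arms. The event is equally likely in each of weeks 1 to 6, so k = 6, 5, ..., 1 weekly contacts remain.
- Each contact finds the event with probability q, independently.
- Every survey is a live call, and the nurse visit is as good as the call at finding events.

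Detected share:
- control = mean over k = 1..6 of 1 − (1 − q)^k
- I-HoME = mean over k = 1..6 of 1 − (1 − q)^(2k)

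An assumed 10% risk in 50 caregivers gives 50 × 0.10 = 5 true events per arm.

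| q | Control share | I-HoME share | Ratio | Recorded of 5, control v I-HoME |
|---|---|---|---|---|
| 0.1 | 0.297 | 0.490 | 1.65 | 1.49 v 2.45 |
| 0.2 | 0.508 | 0.724 | 1.43 | 2.54 v 3.62 |
| 0.3 | 0.657 | 0.842 | 1.28 | 3.28 v 4.21 |
| 0.5 | 0.836 | 0.944 | 1.13 | 4.18 v 4.72 |
| 0.8 | 0.958 | 0.993 | 1.04 | 4.79 v 4.97 |
| 0.9 | 0.981 | 0.998 | 1.02 | 4.91 v 4.99 |
| 1.0 | 1.000 | 1.000 | 1.00 | 5.00 v 5.00 |

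The largest gap in the table is 3.62 − 2.54 = 1.08 events, and at q = 0.9 it is 4.99 − 4.91 = 0.08. At a 20% risk (10 true events per arm) the gaps double and the ratios do not change.

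**Weblink surveys.** A weblink survey with no event item gives the team little from which to identify an event. Suppose half of the surveys in both arms are live, and each live contact has q = 0.5.
- Weekly detection, control: 0.5 × 0.5 = 0.25.
- Weekly detection, I-HoME: 1 − (1 − 0.25)(1 − 0.5) = 0.625.
- Shares over the same six weeks: 0.59 v 0.90, a ratio of about 1.5, or 2.9 v 4.5 of 5 true events. The all-phone ratio at q = 0.5 is 1.13.

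**With a scripted query.** If the shared survey finds 90% of events and a nurse visit 50%, the shares are 0.981 v 0.991, a ratio of 1.01. If the shared survey finds all of them, the ratio is 1.00.

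**The case against.** The best case against the point is that both arms already have the same weekly assessments, and A.1 names follow-up assessments as a place where events are found. The listed events are major ones that a weekly call may well uncover, and the table shows the gap nearly vanishing when it does. This stands as a limit on size. It does not remove the point, because the plan does not say that the call asks.

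A reader might go further than the documents allow in four ways.
- *That counts are bound to differ.* They need not; it depends on how well the shared assessment finds events.
- *That controls have no way to reach the team.* The Aim 3 control paragraph is silent on this; it does not exclude it. Section A.3 says the consent form gives study contact details and does not limit this to one arm. What I-HoME caregivers have is technical assistance, which the text extends to adverse events.
- *That a control answering by weblink has no live contact after baseline.* This is an extreme case. Weblink is an option open to both arms, the Aim 3 measurements text describes phone surveys, and no uptake figure is given.
- *That no event question exists.* Appendix B is not in the text available, and A.2 mentions an Alert/Adverse Event Form in REDCap. That form is described as a place to record an identified event, not as a prompt to the caregiver, but a prompt in the call script cannot be ruled out.

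It is also fair that no by-arm event analysis is planned, that no interim analysis is planned (section B), and that the quarterly summary in A.1 is confined to anticipated, study-related events. The PHQ-9 safeguard in the risk/benefit section addresses suicidality without distinction of arm; the point here concerns the medical events.

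**Conclusion.** The point holds in a limited form. As written, the plan does not secure equal ascertainment of caregiver events. The likely direction is more recorded events in I-HoME and some missed in control. Under the assumed model with weekly calls in both arms, the ratio runs from about 1.65 (q = 0.1) to 1.02 (q = 0.9). The absolute gap at 10% true risk is about 1 event or less per arm, and double that at 20%. With half of the surveys by weblink and q = 0.5, the ratio is about 1.5. These are illustrations: they assume a full six-week course, independent contacts, and a nurse interventionist who passes on events. The documents do not state that last point outright, though they call the interventionist a research nurse.

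The consequence is modest because no formal arm comparison is planned. It is still worth correcting, because the monitor may see grouped data, each meeting must end in a recommendation, and the remedy is cheap. If Appendix B already contains an event query used in both arms and both modes, the main gap closes and A.1 should cite it.

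**What to change.** - Add fixed yes/no questions to every weekly and final caregiver survey, in both arms and in both phone and weblink modes. They should cover caregiver hospitalization, institutionalization, emergency room visit and severe medical problem since the last survey. A yes by weblink should alert the research assistant. A caregiver's death cannot be self-reported, so missed surveys should be followed up in the same way in both arms.
- Record the source of each event on the Alert/Adverse Event Form: shared survey, tele-visit, technical assistance or other.
- Base any by-arm summary for the safety monitor on events from the shared questions. List separately the events found only at tele-visits or through technical assistance. Detection in the summary is then equal by design, provided that survey completion is similar, so report completion by arm beside it.
- State in the control paragraph the same contact route for adverse events that the intervention paragraph gives.

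The cost is about a minute per survey and an edit to the REDCap forms, with no new visits or staff. More events will be recorded, probably mainly in controls. The Aim 4 rationale refers to data already collected. For caregivers already followed, the questions cannot be added, but the source of each recorded event can be coded where known and the limitation stated.
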